6.1. Endpoints

6.1.1. Primary Endpoints

The primary efficacy endpoint is time to any SLE Flare Index flare.

6.1.2. Secondary Endpoints

The secondary endpoints are:

- Rate of any SLE Flare Index flares.
- Time to first severe SLE Flare Index flare.
- Number of subjects in the treatment holiday and long-term discontinuation group with evidence of rebound (defined as a SELENA SLEDAI score during the first 24 weeks that exceeds the baseline SELENA SLEDAI score in the original parent study.
- Number of subjects with confirmed true positive belimumab anti-drug antibodies (ADA) by the end of the study.
- Percentage change from baseline in:
 - Total serum immunoglobulin (IgG, and other isotypes: IgM and IgA)
 - Autoantibodies (anti-dsDNA, ANA), and complement (C3, C4)
- Percent change in absolute B cell subsets (CD20+, CD20+/27+ memory, CD20+/27naïve, CD20+/69+ activated, CD20+/138+ plasmacytoid, CD19+/27BRIGHT/38BRIGHT SLE subset and CD20-/138+ plasma cells) at Weeks 0, 8, 16, 24, 32, 40 and 52 and from Weeks 24 to 52.
- Absolute change in SELENA SLEDAI score.
- Number of days of daily prednisone dose ≥7.5 mg/day and/or increased by 25% from Day 0 of this study to Week 24, from Day 0 of this study to Week 52, and from Week 24 to Week 52.
- Number of days of daily prednisone dose ≤7.5 mg/day and/or decreased by 25% from Day 0 of this study to Week 24, from Day 0 of this study to Week 52, and from Week 24 to Week 52.

Note: baseline is the time before any treatment with belimumab, which was Day 0 of the original parent studies that fed into the 3 continuation studies from which subjects were recruited into this study. When Day 0 is used in relation to endpoints, this refers to Day 0 of this study.

6.1.3. Other Endpoints

- Change in SLICC/ACR Damage Index.
- Percentage change in PGA.
- Percentage change from baseline of prednisone dose at each scheduled visit.

• Percentage of subjects whose average prednisone dose was reduced to ≤7.5 mg/day from >7.5 mg/day at baseline.

6.1.4. Definitions of SLE Flares Used in This Study

SLE flares are defined as:

• SFI Flare: A mild/moderate or severe flare according to the modified SELENA SLEDAI SLE Flare Index (modified excludes severe flares from the SELENA SLEDAI flare assessment that were triggered only by an increase in SELENA SLEDAI score to >12).

A SLE renal flare is defined as the occurrence of 1 or more of the following in 2 or more consecutive visits during the study:

- 1. A reproducible increase in 24-hour urine protein equivalent levels to
 - >1 g if the Day 0 value was <0.2 g,
 - >2 g if the Day 0 value was 0.2 to 1 g, or
 - More than twice the value at Day 0 if the Day 0 value is >1 g.
- A reproducible increase in GFR of >20% accompanied by at least one of the following: proteinuria (>1 g/24 hour equivalent), and/or cellular (RBC or WBC) casts [Alarcón-Segovia, 2003].

6.2. Critical Baseline Assessments

The screening phase of up to 30 days will allow an assessment of the SELENA SLEDAI score as part of the eligibility criteria for subjects in the treatment holiday and control groups.

The EXIT visit of the relevant SLE continuation protocol (BEL114333, HGS1006-C1066, or LBSL99) from which the subject is recruited will serve as the Day 0 visit in this study. Subjects in the control group will be dosed with belimumab at the Day 0 visit as part of this protocol. These subjects must be able to receive the Day 0 dose in this study 4 weeks (minimum of 2 weeks, maximum of 8 weeks) after the last dose in the previous open-label continuation study. Any procedures from this protocol or from the relevant previous open-label continuation protocols to be performed pre-dose must be completed before dosing subjects in the control group. Obtain written informed consent from all subjects to participate in this study at the Screening visit.

Procedures necessary for the Day 0 visit of this protocol and for the last visit of the relevant SLE open-label continuation protocol from which the subject is recruited need only be performed once. Results from Day 0 procedures that are duplicated in the relevant SLE continuation study will be recorded in the eCRF for that study and must also be **transcribed** to the relevant eCRFs in this study. Additional Day 0 procedures exclusive to this study will be recorded directly in the eCRFs for this study.

6.3. Efficacy

Efficacy will be assessed from SELENA SLEDAI score, SLE flare index, Physician's Global Assessment (PGA) and SLICC/ACR damage index.

All site staff scoring SELENA SLEDAI assessments are required to pass proficiency tests before carrying out assessments to ensure consistency across centres.

6.3.1. SELENA SLEDAI

6.3.1.1. SELENA SLEDAI Score

The SELENA SLEDAI (Systemic Lupus Erythematosus Disease Activity Index) used in this study is a slightly modified version of the SLEDAI developed for a National Institutes of Health sponsored multicentre study of estrogen/progesterone hormone use in women with SLE [Buyon, 2005; Petri, 2005]. The descriptions for some of the items are slightly modified, but the organ systems and weighted scores are the same as the published SLEDAI.

The SLEDAI is a validated index for assessing SLE disease activity [Bombardier, 1992]. It is a weighted index in which signs and symptoms, laboratory tests, and physician's assessment for each of 9 organ systems are given a weighted score and summed, if present at the time of the visit or in the preceding 10 days:

- Score of 8 each for CNS and vascular items.
- Score of 4 each for renal and musculoskeletal items.
- Score of 2 each for serosal, dermal, and immunologic items.
- Score of 1 each for constitutional and hematologic items.

The maximum theoretical score for the SELENA SLEDAI is 105 (all 24 descriptors present simultaneously) with 0 indicating inactive disease. A copy of the index is provided in Appendix 1.

Completion of the index requires collection of a 24-hour urine sample for assessment of proteinuria (although spot urine protein:creatinine ratio is commonly substituted in practice), measurement of anti-dsDNA, C3, C4, haematology, and urinalysis, and for subjects with myosis, CPK.

However, spot urine protein:creatinine ratio will be used for determining proteinuria for the SELENA SLEDAI in this study since there is a strong correlation between the protein content of a 24-hour urine collection and the protein:creatinine ratio in a single urine sample [Ginsberg, 1983; Ruggenenti, 1998; Clinical Practice Guidelines for Chronic Kidney Disease, 2002; Price, 2005].

Scoring for proteinuria in the SELENA SLEDAI disease activity index will be in accordance with the following guidelines.

Scoring for Proteinuria at Screening for Eligibility

The proteinuria score for SELENA SLEDAI must be 0 at the most recent assessment performed in BEL114333. If at the screening visit the assessment of 24-hour proteinuria (by spot urine protein to creatinine ratio) shows >0.5 g/24 hour equivalent increase above the previous value (in BEL114333) or the subject develops new onset of proteinuria >0.5 g/24 hour equivalent, 4 points will be assigned at the screening assessment.

Scoring for Proteinuria at Day 0 and Subsequent Study Visits

According to the SELENA SLEDAI scoring rules, unless the proteinuria continues to rise such that it has increased by > 0.5 g/24 hour equivalent at Day 0 (i.e., baseline), the subject, by default, will have an improving SELENA SLEDAI score. This is problematic for data analysis since the percent change in the disease activity scales are calculated from the baseline (not screening) SELENA SLEDAI score. As such, the following scoring rules will be applied:

• Scoring for a Subject with 0 Points for Proteinuria in SELENA SLEDAI

If the proteinuria score for SELENA SLEDAI is 0 and at the subsequent visit the assessment of 24-hour proteinuria (by spot urine protein to creatinine ratio) shows >0.5 g/24 hour equivalent increase above the previous value or the subject develops new onset of proteinuria >0.5 g/24 hour equivalent, 4 points will be assigned at this current visit.

• Scoring for a Subject with Proteinuria and 4 Points Assigned in SELENA SLEDAI

If there is an increase from the last visit of >0.5 g/24 hour equivalent, only 4 points for proteinuria will continue to be applied (so no subject can get more than 4 points for proteinuria at any 1 time point).

If the proteinuria has not improved (i.e., there has not been a decrease in proteinuria of >0.5 g/24 hour equivalent) since the previous assessment, then 4 points will continue to be assigned on the SELENA SLEDAI index at the current visit.

If proteinuria has improved (decrease of >0.5 g/24 hour equivalent or a decrease to ≤ 0.5 g/24 hour equivalent) from the previous visit to the current visit, then 0 points will be assigned on the SELENA SLEDAI index at the current visit.

6.3.1.2. Laboratory tests for SELENA SLEDAI

A strong correlation has been demonstrated between the protein content of a 24-hour urine collection and the protein:creatinine ratio in a single urine sample [Ginsberg, 1983; Ruggenenti, 1998; Clinical Practice Guidelines for Chronic Kidney Disease, 2002; Price, 2005]. For this reason, spot urine protein:creatinine ratio will be used for determining proteinuria in this study for the SELENA SLEDAI disease activity indices.

Measurement of creatinine clearance (CrCl)/glomerular filtration rate (GFR) using timed (for example, 24-hour) urine collections is time consuming and error prone and has consistently been shown to be no more, and often less, reliable than serum creatinine based equations for the estimation of GFR [Clinical Practice Guidelines for Chronic Kidney Disease, 2002]. Therefore, GFR estimated by the Cockroft-Gault formula will be used as was done in the Phase II trial of belimumab (LBSL02) and Phase III.

Cockroft-Gault Equation [Cockcroft, 1976]

$$Cl_{cr}(mL/\min) = \frac{(140 - age(yrs))xweight(kg)}{72xserumcreatinine(mg/dL)} \times 0.85 \text{ if female}$$

Values outside the reference laboratory normal range that require the investigator's assessment of relationship to SLE:

6.3.1.3. SLE Flare Index

The SLE Flare Index categorizes SLE flare as "mild or moderate" or "severe" based on a positive assessment for at least one of 5 variables [Buyon, 2005; Petri, 2001; Petri, 2005].

- Change in SELENA SLEDAI score from the most recent assessment to current (not used for severe flare).
- Change in signs or symptoms of disease activity.
- Change in prednisone dosage.
- Use of new medications for disease activity or hospitalization.
- Change in PGA score.

Hospitalization for SLE activity is an additional category included only for a severe flare.

A copy of the SLE Flare Index is provided in Appendix 1.

6.3.1.4. Physician's Global Assessment (PGA)

The PGA is part of the validated SELENA SLEDAI index and is designed for the physician to indicate the subject's overall disease activity at a particular visit [Petri, 1999]. The PGA is a 0-10 cm visual analogue scale (VAS), anchored at 0 (none) and 3 (severe), with intermediate lines at 1 (mild), and 2 (moderate). Each PGA measurement will be transformed linearly (x 3/10) to obtain a value between 0.00 and 3.00.

The same primary investigator or same subinvestigator will evaluate and score the PGA for the subject each time, unless agreed otherwise with the GSK medical monitor.

A copy of the PGA VAS is provided in Appendix 1.

6.3.2. SLICC/ACR Damage Index

The Systemic Lupus International Collaborative Clinics/American College of Rheumatology (SLICC/ACR) Damage Index is a validated instrument developed to assess the accumulated damage in patients with SLE, resulting from either the disease process or its sequelae. It can identify changes in damage seen in patients with both active and inactive disease and records damage occurring in patients with SLE regardless of its cause [Gladman, 1996]. The index is a predictor of severe outcome and an indicator of morbidity in different ethnic groups [Stoll, 1996]. SLICC/ACR Damage Index was designed to be useful both as a descriptor for patient populations included in studies, and as an outcome measure for therapeutic trials and studies of prognosis [Gladman, 1996].

The SLICC/ACR Damage Index consists of 39 items in 12 different organ systems. For a feature to represent damage, it must be present for at least 6 months, to enable discrimination between active inflammation and tissue damage [Gladman, 1996]

Scoring is usually 0 or 1, although in 6 items, a score of 2 can be given if there is a repeat episode more than 6 months apart. The exception is end-stage renal disease, which scores 3.

A copy of the SLICC/ACR Damage Index is provided in Appendix 2.

6.4. Safety

The safety assessments are adverse events (AEs) (including infusion-related and hypersensitivity reactions, infections and malignancies), haematological and clinical chemistry parameters, urinalysis, B cell markers, immunogenicity, vital signs (including weight), and physical examinations.

6.4.1. Liver chemistry stopping and follow up criteria

Phase III-IV liver chemistry stopping and follow up criteria have been designed to assure subject safety and evaluate liver event etiology (in alignment with the FDA premarketing clinical liver safety guidance) [James, 2009; Le Gal, 2005]. For subjects in the treatment holiday group having belimumab therapy re-introduced from Week 24 onwards or escaping to the maintenance phase of the study prior to Week 24, subjects in the control group, or any subject entering the maintenance phase of the study, the following applies:

Phase III-IV liver chemistry stopping criteria 1-5 are defined below and in Appendix 3:

CONFIDENTIAL

1. ALT \ge 3xULN and bilirubin \ge 2xULN (>35% direct bilirubin) (or ALT \ge 3xULN and INR>1.5, if INR measured)

NOTE: if serum bilirubin fractionation is not immediately available, withdraw belimumab for that subject if $ALT \ge 3xULN$ and bilirubin $\ge 2xULN$. Serum bilirubin fractionation should be performed if testing is available. If testing is unavailable, **record presence of detectable urinary bilirubin on dipstick**, indicating direct bilirubin elevations and suggesting liver injury.

2. ALT \geq 8xULN.

3. ALT \ge 5xULN but <8 xULN persists for \ge 2 weeks OR ALT \ge 3xULN but <5 xULN persists for \ge 4 weeks

4. ALT \ge 3xULN if associated with symptoms (new or worsening) believed to be related to hepatitis (such as fatigue, nausea, vomiting, right upper quadrant pain or tenderness, or jaundice) or hypersensitivity (such as fever, rash or eosinophilia).

5. ALT \ge 5xULN but <8 xULN and cannot be monitored weekly for \ge 2 weeks OR ALT \ge 3xULN but <5 xULN and cannot be monitored weekly for \ge 4 weeks

When any of the liver chemistry stopping criteria 1-5 is met, do the following:

- Immediately discontinue belimumab for that subject
- Report the event to GSK within 24 hours
- Complete the liver event CRF and SAE data collection tool if the event also meets the criteria for an SAE. All events of ALT ≥ 3xULN and bilirubin ≥ 2xULN (>35% direct) (or ALT ≥ 3xULN and INR>1.5, if INR measured); INR measurement is not required and the threshold value stated will not apply to patients receiving anticoagulants), termed 'Hy's Law', must be reported as an SAE (excluding studies of hepatic impairment or cirrhosis).

NOTE: if serum bilirubin fractionation is not immediately available, withdraw belimumab for that subject if $ALT \ge 3xULN$ and bilirubin $\ge 2xULN$. Serum bilirubin fractionation should be performed if testing is available. If testing is unavailable, record presence of detectable urinary bilirubin on dipstick, indicating direct bilirubin elevations and suggesting liver injury.

- Complete the liver imaging and/or liver biopsy CRFs if these tests are performed
- Perform liver event follow up assessments, and monitor the subject until liver chemistries resolve, stabilize, or return to baseline values as described below.
- Do not restart subject with belimumab unless GSK Medical Governance approval is granted (refer to Section 6.4.1.1)

Monitoring for liver chemistry stopping criterion 1:

• Make every reasonable attempt to have subjects return to clinic within **24 hours** for repeat liver chemistries, liver event follow up assessments (see below), and close monitoring

- A specialist or hepatology consultation is recommended
- Monitor subjects twice weekly until liver chemistries (ALT, AST, alkaline phosphatase, bilirubin) resolve, stabilize or return to within baseline values

Monitoring for liver chemistry stopping criteria 2, 3, 4 and 5:

- Make every reasonable attempt to have subjects return to clinic **within 24-72 hrs** for repeat liver chemistries and liver event follow up assessments (see below)
- Monitor subjects weekly until liver chemistries (ALT, AST, alkaline phosphatase, bilirubin) resolve, stabilize or return to within baseline values; criterion 5 subjects should be monitored as frequently as possible.

Phase III-IV Liver Chemistry Increased Monitoring Criteria With Continued Therapy

Subjects with ALT \geq 5xULN and <8xULN **and** bilirubin <2xULN **without** symptoms believed to be related to liver injury or hypersensitivity, and who can be monitored weekly for 2 weeks OR ALT x \geq 3xULN, but <5xULN and bilirubin <2xULN **without** symptoms believed to be related to liver injury or hypersensitivity, and who can be monitored weekly for 4 weeks:

- Notify the GSK medical monitor **within 24 hours** of learning of the abnormality to discuss subject safety
- Can continue belimumab
- Must return weekly for repeat liver chemistries (ALT, AST, alkaline phosphatase, bilirubin) until they resolve, stabilize or return to within baseline
- If at any time these subjects meet the liver chemistry stopping criteria, proceed as described above
- If ALT decreases from ALT \geq 5xULN and \leq 8xULN to \geq 3xULN but \leq 5xULN, continue to monitor liver chemistries weekly.
- If, after 4 weeks of monitoring, ALT <3xULN and bilirubin <2xULN, monitor subjects twice monthly until liver chemistries normalize or return to within baseline values.

Follow-up Assessments For Liver Stopping Criteria 1-5

Make every attempt to carry out the liver event follow up assessments described below:

- Viral hepatitis serology including:
 - Hepatitis A IgM antibody;
 - Hepatitis B surface antigen and Hepatitis B Core Antibody (IgM);
 - Hepatitis C RNA;
 - Cytomegalovirus IgM antibody;

- Epstein-Barr viral capsid antigen IgM antibody (or if unavailable, obtain heterophile antibody or monospot testing);
- Hepatitis E IgM antibody
- Only in those with underlying chronic hepatitis B at study entry (identified by positive hepatitis B surface antigen): quantitative hepatitis B DNA and hepatitis delta antibody. **NOTE**: if hepatitis delta antibody assay cannot be performed, it can be replaced with a PCR of hepatitis D RNA virus (where needed) [Le Gal, 2005].
- Blood sample for PK analysis, obtained within approximately one to two weeks after the liver event. Record the date/time of the PK blood sample draw and the date/time of the last dose of belimumab prior to blood sample draw on the CRF. If the date or time of the last dose is unclear, provide the subject's best approximation. If the date/time of the last dose cannot be approximated OR a PK sample cannot be collected in the time period indicated above, do not obtain a PK sample. Instructions for sample handling and shipping are in the SPM.
- Serum creatine phosphokinase (CPK) and lactate dehydrogenase (LDH).
- Fractionate bilirubin, if total bilirubin $\geq 2xULN$.
- Obtain complete blood count with differential to assess eosinophilia.
- Record the appearance or worsening of clinical symptoms of hepatitis or hypersensitivity, such as fatigue, nausea, vomiting, right upper quadrant pain or tenderness, fever rash or eosinophilia as relevant on the AE report form.
- Record use of concomitant medications, acetaminophen, herbal remedies, other over the counter medications, or putative hepatotoxins, on the concomitant medications report form.
- Record alcohol use on the liver event alcohol intake case report form.

The following are required for subjects with ALT $\ge 3xULN$ and bilirubin $\ge 2xULN$ (>35% direct) or ALT $\ge 3xULN$ and INR>1.5, if INR measured; but are optional for other abnormal liver chemistries:

- Anti-nuclear antibody, anti-smooth muscle antibody, and Type 1 anti-liver kidney microsomal antibodies, and quantitative total immunoglobulin G (IgG or gamma globulins).
- Serum acetaminophen adduct HPLC assay (quantifies potential acetaminophen contribution to liver injury in subjects with definite or likely acetaminophen use in the preceding week [James, 2009]). **NOTE: not required in China.**
- Liver imaging (ultrasound, magnetic resonance, or computerized tomography) to evaluate liver disease.

For long-term discontinuation group subjects found to have met the liver stopping criteria without receiving belimumab, investigators will apply the withdrawal criteria in Section 4.4.

6.4.1.1. Study Treatment Restart

If subject meets liver chemistry stopping criteria do not restart subject with study treatment unless:

- GSK Medical Governance approval is granted (as described below),
- Ethics and/or IRB approval is obtained, if required, and
- Separate consent for treatment restart is signed by the subject

If GSK Medical Governance approval to restart subject with study treatment is not granted, then subject must permanently discontinue study treatment and may continue in the study for protocol-specified follow up assessments.

Restart Following Transient Resolving Liver Stopping Events Not Related to Study Treatment

Restart refers to resuming study treatment following liver stopping events in which there is a clear underlying cause (other than drug induced liver injury [DILI]) of the liver event (e.g. biliary obstruction, pancreatic events, hypotension, acute viral hepatitis). Furthermore, there should be no evidence of alcoholic hepatitis or hypersensitivity, and the study treatment should not be associated with HLA markers of liver injury.

Approval by GSK for study treatment restart can be considered where:

- Investigator requests consideration for study treatment restart if liver chemistries have a clear underlying cause (e.g., biliary obstruction, hypotension and liver chemistries have improved to normal or are within 1.5 x baseline and ALT <3xULN).
- Restart risk factors (e.g., fever, rash, eosinophilia, or hypersensitivity, alcoholic hepatitis, possible study treatment-induced liver injury or study treatment has an HLA genetic marker associated with liver injury (e.g., lapatinib, abacavir, amoxicillin/clavulanate) are reviewed and excluded
- Ethics Committee or Institutional Review Board approval of study treatment restart must be obtained, as required.
- If restart of study treatment is approved by GSK Medical Governance in writing, the subject must be provided with a clear description of the possible benefits and risks of study treatment administration, including the possibility of recurrent, more severe liver injury or death.
- The subject must also provide signed informed consent specifically for the study treatment restart. Documentation of informed consent must be recorded in the study chart.
- Study treatment must be administered at the dose specified by GSK.
- Subjects approved by GSK Medical Governance for restarting study treatment must return to the clinic once a week for liver chemistry tests until stable liver chemistries have been demonstrated and then laboratory monitoring may resume as per protocol.

- If after study treatment re-start, subject meets protocol-defined liver chemistry stopping criteria, follow usual stopping criteria instructions.
- GSK Medical Monitor, and the Ethics Committee or Institutional Review Board as required, must be informed of the subject's outcome following study treatment restart.
- GSK to be notified of any adverse events, as per Section 6.4.7.

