4.4. Withdrawal Criteria

A subject may voluntarily discontinue participation in this study at any time or may be withdrawn at the discretion of the investigator. Record the primary reason for withdrawal in the electronic case report form (eCRF).

Subjects in the treatment holiday and control groups will be withdrawn from the study for:

- Pregnancy: positive urine pregnancy test.
- Clinically significant, potentially life-threatening (Grade 4) AE that in the clinical judgement of the investigator is possibly, probably or definitely related to belimumab.
- Liver chemistry abnormalities. Refer to details regarding liver chemistry abnormalities and withdrawal as specified in Section 6.4.1.

- Laboratory parameters: Demonstrate clinically important changes in laboratory parameters.
- Prohibited concurrent medication or therapy.

These subjects will complete the Week 52 Exit visit (except for dosing with belimumab) at the time of discontinuation and the16-week follow-up visit assessments at least 16 weeks after the withdrawal visit or last dose of belimumab as appropriate (see Section 6). The 6 month follow-up visit is scheduled only for those subjects in the treatment holiday or control groups.

Subjects in the long-term discontinuation group will be withdrawn from the study for:

- Pregnancy: positive urine pregnancy test.
- Laboratory parameters: Demonstrate clinically important changes in laboratory parameters.
- Have developed clinical evidence of significant, unstable or uncontrolled, acute or chronic diseases not due to SLE (i.e., cardiovascular, pulmonary, hematologic, gastrointestinal, hepatic, renal, neurological, malignancy or infectious diseases), or experienced an adverse event (AE) that could, in the opinion of the principal investigator, put the subject at undue risk.
- Have developed any other medical diseases (e.g., cardiopulmonary), laboratory abnormalities, or conditions (e.g., poor venous access) that, in the opinion of the principal investigator, makes the subject unsuitable for the study.

These subjects will complete the Week 52 visit assessments (see Section 6).

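### After a liver stopping event, Protocol 4.4 takes the subject out of the study, while 6.4.1 and 6.4.1.1 only stop belimumab and allow it to be restarted

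*Protocol*

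**What the plan says.** Protocol 4.4 opens a list with "Subjects in the treatment holiday and control groups will be withdrawn from the study for". One item on it is "Liver chemistry abnormalities. Refer to details regarding liver chemistry abnormalities and withdrawal as specified in Section 6.4.1". The consequence follows the list: "These subjects will complete the Week 52 Exit visit (except for dosing with belimumab) at the time of discontinuation", then the 16-week and 6-month follow-up visits. Protocol Section 6 puts this into operation by sending any holiday or control subject who meets a 4.4 criterion to the Exit visit, in Year 1 or later.

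Protocol 6.4.1 gives the actions when any of stopping criteria 1–5 is met. They include "Immediately discontinue belimumab for that subject", reporting, liver follow-up and monitoring, and "Do not restart subject with belimumab unless GSK Medical Governance approval is granted". None of them removes the subject from the study.

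Protocol 6.4.1.1 has two branches:
- **Restart approved:** "Restart refers to resuming study treatment following liver stopping events in which there is a clear underlying cause". Weekly liver tests follow until stable, and the usual monitoring then resumes.
- **Restart not approved:** "then subject must permanently discontinue study treatment and may continue in the study for protocol-specified follow up assessments".

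The endpoint rules depend on study withdrawal:
- **Primary endpoint:** a flare-free subject who withdraws is censored at the last flare assessment (Protocol 8.1.2, SAP 7.1.4).
- **Flare rate:** withdrawal counts as a flare (SAP 7.2.4.1 and 13.7.3).
- **Prednisone-day endpoints:** days after dropout are imputed unfavourably (SAP 7.2.4.3).
- **Disposition:** derived from the recorded completion status (SAP 13.6.2).

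**The concern.** One liver event leads to two different study statuses, depending on which section the site follows. Under 4.4 the subject exits. Under 6.4.1 and 6.4.1.1 the subject stops belimumab, remains under the protocol and may be dosed again.

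Two things are at stake. The first is safety observation: sites may follow comparable subjects for different lengths of time and on different schedules. The second is the analysis. The status recorded by the site decides whether the subject is censored early, given an imputed flare and imputed unfavourably on prednisone, or contributes whatever is observed. In groups of 12 and 29 subjects, one such decision is visible in the flare rate.

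**Working it through.** **The texts compared**

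| Question | 4.4 and Section 6 | 6.4.1 | 6.4.1.1 |
|---|---|---|---|
| What stops? | Study participation | Belimumab | Belimumab, for good if restart is refused |
| Can dosing resume? | No; Exit visit, then follow-up visits | Yes, with approval | Yes, with approval |
| Is the subject still in the study? | No | Not stated | Yes if restarted; may remain if refused |

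1. *Restart branch.* Resumed dosing and monitoring require a subject who is still on study. This cannot be combined with 4.4.
2. *Not-approved branch.* The assessments meant are not named. If they are the Exit, 16-week and 6-month visits, this branch agrees with 4.4. If they are the remaining scheduled visits to Week 52, it does not.
3. *Cross-reference.* 4.4 defers to 6.4.1 for withdrawal details, but current 6.4.1 has no study-withdrawal rule for these groups. The conflict is therefore in current text. The Amendment 04 log shows a study-withdrawal instruction struck out of 6.4.1, which may explain how the mismatch arose but is not itself an error.
4. *Who is covered.* For the holiday group, 6.4.1 begins "For subjects in the treatment holiday group having belimumab therapy re-introduced from Week 24 onwards" and adds those who escape earlier. Holiday subjects still off drug are outside it. Enrolment was 12 holiday and 29 control (SAP 2.3), so the ceiling is 12 + 29 = 41.
5. *Flare observation.* In Protocol Table 2, flare is assessed up to Week 52 or Exit and not at the 16-week or 6-month visit. Exit under 4.4 therefore ends flare observation.

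**Size of one event**

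The plan gives no liver-event rate and no figure to reproduce, so this is an illustration. The formula, from SAP 13.6.3, is rate = flares ÷ subject-years, with days divided by 365.25. Assumptions:
- one event, in a subject with no flare;
- everyone else completes;
- the event falls 28 to 168 days into the phase;
- a retained subject is followed to Week 52;
- all 12 holiday subjects enter the re-start phase.

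*Holiday re-start phase* (364 − 168 = 196 days per subject)
- Retained: 12 × 196 / 365.25 = 6.44 subject-years, no flare added.
- Withdrawn at day 28: (11 × 196 + 28) / 365.25 = 5.98; 1 / 5.98 = 0.167.
- Withdrawn at day 168: (11 × 196 + 168) / 365.25 = 6.36; 1 / 6.36 = 0.157.

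*Control group* (365 days per subject)
- Retained: 29 × 365 / 365.25 = 28.98 subject-years, no flare added.
- Withdrawn at day 28: (28 × 365 + 28) / 365.25 = 28.06; 1 / 28.06 = 0.036.
- Withdrawn at day 168: (28 × 365 + 168) / 365.25 = 28.44; 1 / 28.44 = 0.035.

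These increments are the contribution of the imputed flare alone. The shorter follow-up also slightly raises the rate from any other flares in the group. A subject who re-starts before Week 24 has no re-start phase (SAP 13.4.1), so the 12 may be fewer, and one imputed flare would then weigh more.

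**The case against.** The best defence is that the 4.4 item is not free-standing. It hands the detail to 6.4.1, which does speak of withdrawing belimumab, so a careful site could treat the specific section as governing. This softens the conflict but does not remove it: the list is headed as withdrawal from the study, Section 6 acts on it, and 6.4.1 contains nothing that turns it into a treatment-only rule.

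Three stronger readings are tempting, and the documents do not support them:
- *That the follow-up sentence in 6.4.1.1 also contradicts 4.4.* It need not. It is permissive, and subjects withdrawn under 4.4 already have protocol follow-up visits. The firm contradiction is the restart branch, and that branch is narrow: it needs a clear cause other than drug-induced liver injury, sponsor approval, ethics approval where required, and separate consent.
- *That a retained subject supplies observed data to Week 52.* This is one reading and is stated nowhere. If only the follow-up visits are meant, the flare difference disappears for the not-approved branch.
- *That all 41 subjects are exposed.* Holiday subjects still off drug fall outside 6.4.1.

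It is also fair to say that the rate effect arises from the SAP rule counting withdrawal as a flare, that the analyses are descriptive only, and that SAP 5.3.1 refers to this study's last patient last visit as already past. Editing the protocol then could not change site conduct. These points limit the consequences. They do not make the text consistent.

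**Conclusion.** The inconsistency is real and present in current text: study withdrawal under 4.4 cannot coexist with the restart path in 6.4.1.1, and the reference to 6.4.1 does not settle the matter. The not-approved branch is ambiguous, not contradictory.

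The effect on results is conditional. It is zero if no liver stopping event occurred in the 52-week phase. Under the stated assumptions, including follow-up of a retained subject to Week 52, one event coded as withdrawal adds about 0.16–0.17 flares per subject-year in the holiday re-start phase or about 0.035 in controls. It also censors that subject early in the primary analysis. A reader might infer that the reported flare rates are biased; the documents give no event count, so they do not support that inference.

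**What to change.** **Protocol.** Reconcile 4.4, 6.4.1 and 6.4.1.1 so that one study status applies after a liver stopping event, and state which assessments the not-approved branch refers to. Which clinical rule is right is for the sponsor; no view is given here.

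**SAP and report.** Check every subject in Listing 40 (liver stopping events) against the recorded completion status and Listing 5 (reasons for study withdrawal), and report which status was applied. Apply the withdrawal rules (censoring, flare imputation and prednisone imputation) only to subjects whose scheduled 52-week visits actually ended. Do not apply them to subjects who stopped or restarted belimumab and stayed on the visit schedule. The test should be the scheduled visits and not follow-up in general, because subjects withdrawn under 4.4 also have follow-up visits.

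**Cost.** One item in 4.4 or the matching sentences in 6.4.1 and 6.4.1.1, one line in SAP 13.7.1, and a cross-check of two listings already planned. No new data are needed.
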